4.2 ANALYSIS OF STUDY CONDUCT

4.2.1 Study Enrollment

The number of patients in each of the ITT and safety populations will be summarized, and the number of patients excluded from each of the populations will be summarized by reason for exclusion.

The number of patients enrolled at each country and site will also be summarized.

4.2.2 Protocol Deviations

The major protocol deviations will be identified according to the Procedures for Managing Protocol Deviations document. The number and percentage of patients with major protocol violations will be summarized by protocol violation criterion.

4.2.3 Patient Disposition

The number and percentage of patients completing and withdrawing from the study and the number and percentage of patients withdrawing from treatment will be summarized. The reasons for premature study or treatment withdrawal will also be summarized.

4.3 ANALYSIS OF TREATMENT GROUP COMPARABILITY

Summary tables of demographics and other baseline characteristics will be produced for the safety population. Summaries will be presented overall and by the treatment received in the previous study. Patients who only participated in study TRO19622CLEQ1115-1 and those who participated in study TRO19622CLEQ1275-1 will be summarized separately.

Where available, similar descriptive statistics will be presented for the historical comparison population and the NatHis-SMA comparison population. Demographic and baseline characteristics (including age, gender, SMA type, country and baseline MFM D1+D2 and total scores) will also be summarized by data source in order to assess potential heterogeneity between the different data sources.

4.3.1 Demographics

Summary statistics will be presented for the following demographic and baseline characteristics: age (at the time of first treatment in the open-label part of the study), sex, race, ethnicity, country, weight, height, body mass index (BMI) and tanner stage (for patients 9-17 years old).

If height cannot be measured directly (e.g. due to scoliosis or contractures) ulnar length will be used to calculate a surrogate height measure. For patients with an ulnar length measurement available and height indicated as 'derived' in the electronic case report form (eCRF), height will be derived from the measurement of ulnar length using the following formulae:

For patients 5-19 years old (Gauld et al. 2004):

$$\text{Female: height (cm)} = 4.459 * \text{ulnar length (cm)} + 1.315 * \text{age (years)} + 31.485$$

$$\text{Male: height (cm)} = 4.605 * \text{ulnar length (cm)} + 1.308 * \text{age (years)} + 28.003$$

For patients > 19 years old (Elia 2003):

$$\text{Female: height (cm)} = 95.6 + 2.77 * \text{ulnar length (cm)}$$

$$\text{Male: height (cm)} = 79.2 + 3.60 * \text{ulnar length (cm)}$$

Percentiles for weight-for-age, stature-for-age, weight-for-stature and BMI-for-age will also be presented for all patients. These will be based on the Centers for Disease Control and Prevention (CDC) growth standards. For patients > 20 years (240 months) old, percentiles will be based on the reference data for individuals 240 months of age. Percentiles for stature-for-age, weight-for-stature and BMI-for-age may be presented separately for patients whose height can be measured directly and those whose height cannot be measured directly.

4.3.2 Baseline Disease Characteristics

Summary statistics will be presented for the following baseline disease characteristics: MFM D1+D2 score, MFM total score, FVC, FVC/TC and HFMS score at baseline. Summary statistics will also be presented for SMA type (data from previous Trophos study) and SMN2 copy number.

4.3.3 General Medical History and Baseline Conditions

For all medical conditions, the term entered by the investigator describing the condition (the 'verbatim term') will be assigned to a standardized term (the 'preferred term') and system organ class based on the most up-to-date version of the Medical Dictionary for Regulatory Activities (MedDRA). All analyses will be performed using these preferred terms and body systems.

The number and percentage of patients with previous conditions and conditions concurrent at baseline will be summarized. Multiple occurrences of the same condition in an individual patient (i.e. same coded term) will be counted only once. Previous conditions (conditions with an end date before the first dose date) and conditions concurrent at baseline (conditions that start prior to first study drug intake and have no end date or an end date after the first dose date) will be summarized separately.

The number and percentage of patients who had any relevant surgeries or procedures will be summarized similarly.

4.3.4 Previous and Concomitant Medications

For all medications, the term entered by the investigator describing the medication (the 'verbatim term') will be assigned to a standardized term (the 'preferred term') and drug class based on the Genentech Drug Thesaurus. All analyses will be performed using these preferred terms and medication classes.

The number and percentage of patients taking each medication will be presented. Multiple occurrences of the same medication in an individual patient (i.e. same coded term) will be counted only once. Previous medications (medications with an end date before the first dose date), medications present at baseline (medications that start prior to first study drug intake and have no end date or an end date after the first dose date) and concomitant medications (medications with a start date on or after the first dose date) will be summarized separately.

4.3.5 SMA Related Exercise and Physical Therapy

The number and percentage of patients prescribed exercise or physical therapy programs that in the opinion of the treating investigator are related to the natural course of SMA will be presented. Previous (programs with an end date before the first dose date) and current (programs with a start date on or after the first dose date) programs will be summarized separately. Programs that start prior to first study drug intake and have no end date or an end date after the first dose date will be counted in the current programs summary table.

4.4 EFFICACY ANALYSIS

As this is a single arm, open-label study no formal hypothesis testing will be performed. Data collected during the treatment phase of this study will be summarized using descriptive statistics and will be compared with observational data describing the natural history of the disease.

The baseline value will be defined as the last non-missing value recorded prior to or on the first day of the study drug (Study Day 1).

Post-baseline efficacy assessments (scheduled every 26 weeks), including assessments performed at an early discontinuation visit, will be assigned to a scheduled study visit based on the following time windows:

Visit	Study Day	Time Window (in Study Days)
V3 (Week 26)	183	Day 2 – Day 274
V5 (Week 52)	365	Day 275 – Day 456
V6 (Week 78)	547	Day 457 – Day 638
V7 (Week 104)	729	Day 639 – Day 820
V8 (Week 130)	911	Day 821 – Day 1002
V9 (Week 156)	1093	Day 1003 – Day 1184
V10 (Week 182)	1275	Day 1185 – Day 1366
V11 (Week 208)	1457	Day 1367 – Day 1548
...		

If multiple valid values for a variable are recorded in the same time window, the record closest to the scheduled study visit will be selected for summary of the data.

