### **3.1.1.2      Screening Period**

After written informed consent from the patient, parent or legal guardian, and if appropriate, assent from the child, is obtained, the patients will be screened for eligibility.

**NB.** Enrollment in the open-label treatment period of the study is independent from Historical Data Collection, and a separate informed consent for the following periods should be signed. It is possible for the patient or legal representative to decline participation in the Historical Data Collection and still be eligible to participate in the open-label period. It is also possible for the patient to decline participation in the open-label period, but still consent to the Historical Data Collection.

The screening period will last a maximum of 6 weeks. Procedures at screening will include: medical examination including a thorough neurological exam, MFM scales, ECG, blood and urine sampling and medical history.

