### **4.4 STUDY ASSESSMENTS**

Please see Appendix 1 for Historical Data Collection.

Laboratory safety samples should be collected first at each visit, *preferably* under fasted conditions. After receiving food, the PRO assessments (in the pre-specified order) should be administered first. Then, all other assessments can be performed in the order convenient for the site. If it is not possible for the patient to perform all assessments during the day, the site may divide the assessments between 2 consecutive days.

At applicable sites, certain study assessments may be performed by a trained home nursing professional (HN) at the patient's home to improve access and convenience for patients participating in the study. The schedule of assessments (see [Appendix 1](#)) will specify the assessments that may be performed by an HN professional.

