#### **4.4.10 Patient-Reported Outcomes**

Patient Reported Outcomes (PRO) data will be collected via questionnaires to more fully characterize the clinical profile of olesoxime. The questionnaires will be in paper format, and translated as required in the local language. To ensure instrument validity and that data standards meet health authority requirements, the questionnaires scheduled for administration during a clinic visit should be completed *after the laboratory safety samples have been taken and prior to administration of study treatment and to the performance of non-PRO assessments, in the order defined below. Where appropriate, both caregiver and patient should complete the PedsQL Generic Core Scales. The self-report version of EQ-5D-5L should be completed by patients ≥12 years of age, and the proxy version completed by caregivers of patients <12 years of age. The SMAIS self-report version should be completed by patients aged ≥12 years, and the SMAIS caregiver-report version should be completed by a caregiver for all patients, where possible. The form used in the baseline assessment should be used at all subsequent visits and the dose increase visit (e.g., patients aged <12 years will not complete the EQ-5D-5L or the SMAIS even if their 12th birthday occurs during the study, and patients aged 8-12 years will continue to use the PedsQL forms for ages 8-12 years even if their 13th birthday occurs during the study).*

The PRO measures for this study are as follows:

- *The EQ-5D-5L conducted at all visits except screening, Visit 2, and Visit 4: The EQ-5D-5L is a self-report health status questionnaire that consists of six questions used to calculate a health utility score for use in health economic analysis (EuroQol Group 1990; Brooks 1996; Herdman et al. 2011; van Hout et al. 2012; Janssen et al. 2013, Oppe et al. 2014). There are two components to the EQ-5D-5L: a five-item health state profile that assesses mobility, self-care, usual activities, pain/discomfort, and anxiety/depression, as well as a visual analog scale (VAS) that measures overall health status. Published weighting systems allow for creation of a single summary score. Overall scores range from 0 to 1, with low scores representing a higher level of dysfunction; for some countries (e.g., United Kingdom), scores below zero are possible. The EQ-5D-5L will be utilized in this study for economic modeling.*

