Descriptive statistics for the actual values and change from baseline values in the MFM D1+D2 score will be presented. The results will be presented according to the timings of the MFM assessment visits in the ITT population: 26, 52, 78, 104 and every 26 weeks thereafter after baseline until the end of the study. As the MFM measurements in the natural history databases were not all collected at specific time points after baseline measurements, the measurements will be assigned to a scheduled study visit based on the time windows defined above. If more than one MFM measurement is recorded in the same time window the assessment closest to the target visit day will be used. Mean changes in the MFM D1+D2 score and corresponding 95% CIs over time will also be presented graphically.

Given sufficient data, the change from baseline in the MFM D1+D2 score at weeks 26, 52, 78 and 104 will also be analyzed using a mixed-effects model for repeated measures (MMRM). The model will include the treatment group, age, gender, SMA type, visit, treatment-by-visit interaction, and the baseline MFM D1+D2 score as covariates. Matched set will be included in the model as a random effect.

An unstructured variance-covariance matrix will be applied to model the within-patient errors. The restricted maximum likelihood method will be used for estimates of variance components. Denominator degrees of freedom will be estimated using the Kenward-Roger approximation. A treatment-by-time interaction contrast will be constructed to estimate the difference between the two groups in the mean change from baseline at each visit, and the 95% CI for the treatment difference will be reported.

If there are a sufficient number of patients in the historical comparison population for one-to-one matching to be performed, but the covariate balance between the treated and untreated groups after matching is worse than the balance before matching, then the optimal full matching described in Section 4.1.4 will be performed, and the covariate balance in this new population will be assessed. If the covariate balance between the treated and untreated groups after optimal full matching is worse than the balance before matching (and worse than the balance after one-to-one matching, if applicable), descriptive statistics for the MFM D1+D2 score will be presented for the historical comparison population, and the treatment effect in the pooled ITT and historical

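### The Week 26 efficacy window reaches back to Day 2, so a control's lone early MFM score can count as 26 weeks of change; separately, a split first visit can leave a treated patient without a baseline

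*SAP*

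**What the plan says.** **Baseline and windows (SAP 4.4).** "The baseline value will be defined as the last non-missing value recorded prior to or on the first day of the study drug", that is, Study Day 1. The efficacy table sets Week 26 (V3) at a target of Day 183 with a window of Day 2 to Day 274. Week 52 (V5), with target Day 365, has "Day 275 – Day 456", and later windows have the same shape. Early-discontinuation assessments go into the same windows. Where several values fall in one window, "the record closest to the scheduled study visit will be selected for summary of the data".

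**Controls (SAP 4.1.3 and 4.4.1.2).** A natural-history patient needs at least two MFM-32 assessments, with no minimum interval between them. The SAP acknowledges that these scores were not all taken at fixed times, and says that "the measurements will be assigned to a scheduled study visit based on the time windows defined above". It adds: "If more than one MFM measurement is recorded in the same time window the assessment closest to the target visit day will be used". Week 26 is both a descriptive time point and one of the four visits in the MMRM.

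**First visit (Protocol).** Section 4.4 says that if a patient cannot manage everything in one day, "the site may divide the assessments between 2 consecutive days"; the baseline visit is not excepted. Section 4.4.10 orders the patient-reported outcomes "prior to administration of study treatment and to the performance of non-PRO assessments", and Appendix 1 marks PK and biomarker samples as predose. Nothing comparable is said for MFM or FVC. Section 3.1.1.2 states "Procedures at screening will include: medical examination including a thorough neurological exam, MFM scales, ECG", among other items, but the MFM row of Appendix 1 starts at the baseline visit.

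**The concern.** A score from the first weeks after baseline carries little information about 26 weeks of change, yet the table labels it Week 26. Treated patients are scheduled at Week 26 within 7 days. Controls were seen at irregular times, so at this visit the two groups may be compared after unequal follow-up. MFM D1+D2 is the SAP's primary efficacy measure, and natural history is its comparator.

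The hard stop at Day 1 raises a second problem. A site that splits the first visit as the protocol allows could dose on the first day and do the MFM on the second. The value intended as baseline would then be a post-baseline value.

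**Working it through.** **Inputs.** The window table is in SAP 4.4. The placebo slope of MFM D1+D2 is -1.05 points/year, with a relative standard error of 27% (Protocol 3.3.1). As an upper illustration I use 2 points/year; Protocol 1.2.4 reports a decline of more than 2 points/year after stopping drug. One raw MFM-32 D1+D2 item point is 100/75 = 1.33 (SAP 4.4.1).

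**1. Reproducing the windows.** Target day = 7 x week + 1, giving 183, 365, 547 and so on to 1457. Each upper limit is the midpoint of adjacent targets: (183 + 365)/2 = 274, (365 + 547)/2 = 456, and so on to 1548. Each lower limit is the previous upper limit plus 1. Every entry from V3 to V11 is reproduced except the V3 lower limit.

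- V5 to V11: 90 days below target, 91 above, 182 days in all.
- V3: 183 - 2 = 181 below, 274 - 183 = 91 above, 273 days in all.
- The midpoint of Day 1 and Day 183 is Day 92, so the SAP's own rule would give Day 93 to Day 274, which is 182 days.
- Days 2 to 92 are 91/273 = 33% of the V3 window. None of them is nearer to Day 183 than to Day 1.

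**2. Who is affected.** A score on Days 2 to 91 is at least 92 days from target. A score on Days 93 to 274 is at most 91 days away. Day 92 ties only with Day 274. An early score is therefore used only if the patient has nothing later in the window. A V3 visit held on schedule (about Days 176 to 190) always displaces it.

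**3. One affected control.** Expected decline by day d = slope x (d - 1)/365, assuming linear decline.

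| Day of only score | Decline at 1.05/year | Share of 26-week decline missed | Decline at 2/year |
|---|---|---|---|
| 30 | 0.08 | 84% | 0.16 |
| 60 | 0.17 | 68% | 0.32 |
| 92 | 0.26 | 50% | 0.50 |
| 183 | 0.52 | 0% | 1.00 |

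**4. The control mean at Week 26.** Suppose a fraction f of controls have only an early score, with mean Day 60 (assumption). Shift = f x slope x (183 - 60)/365.

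- At 1.05/year: f x 0.354, so 0.04 at 10% and 0.14 at 40%.
- At 2/year: f x 0.674, so 0.07 at 10% and 0.27 at 40%.

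A different assumption is that every control has one score, spread evenly over the window. The mean day is then 138 and the expected decline at 1.05/year is 1.05 x 137/365 = 0.39, against 0.52 at Day 183. With a window of Days 93 to 274 the mean day is 183.5 and the decline is 0.53 (0.525 before rounding).

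**5. The split first visit.** Four things must coincide: the visit is split, the first dose is on the first day, MFM or FVC is on the second, and no earlier value exists. The second-day value is then Day 2, which is post-baseline and inside the Week 26 window. The patient has no baseline and so no change score at any visit, and cannot be matched on baseline MFM D1+D2 (SAP 4.1.4). For MFM, whether an earlier value exists depends on which of Protocol 3.1.1.2 and Appendix 1 is followed. For FVC, neither lists a screening measurement. The Day 2 MFM would also satisfy the ITT requirement of one post-baseline MFM (SAP 4.1.1).

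**The case against.** The closest-record rule does most of the work that a tighter window would do. A reader might infer from the table that any Day 2 score becomes the Week 26 value, or that early control scores routinely stand in for Week 26. The documents do not support that: both happen only when nothing later falls in the window.

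The lost-baseline route is a chain of conditions. Study Day 1 is the first day of drug, not the date of the first visit, so if dosing waits for the second day, that day's MFM is baseline. If MFM is done at screening, a baseline exists. Even without one, absolute MFM values are still summarized. Patient-reported outcomes are already ordered before dosing, so they need no new rule.

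The control effect is small. The 0.14-point upper figure is about a tenth of one item point, and no larger than the uncertainty in the slope itself over 26 weeks (0.27 x 1.05 x 182/365 = 0.14). The SAP plans no formal hypothesis test. The safety table also opens its first window on Day 2, although its first target is Day 92, so its earliest record is 90 days off target rather than 181. Finally, a Day 93 cut would remove some early leavers' only post-baseline MFM, while SAP 4.4.1.1 says that all observed assessments enter the analyses.

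All of this stands as a limit on size and scope. It does not remove the unequal follow-up for controls with only an early score, and the closest-record rule cannot restore a missing baseline. The conflict with 4.4.1.1 must be handled in the fix.

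**Conclusion.** The point holds in limited form. The V3 window departs from the SAP's own midpoint rule, and applying it to irregularly timed controls lets a Day 2 to 92 score be reported and modelled as 26 weeks of change when it is the control's only score in the window. The direct effect is confined to Week 26.

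The direction matters. A reader might suspect that the window flatters olesoxime, but early scores make untreated patients look more stable, so the error works against the drug.

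The shift of 0.04 to 0.14 points rests on the -1.05 slope, linear decline, and an assumed 10% to 40% of controls with mean Day 60. The documents do not give the timing of control assessments, so the true size is unknown.

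The baseline gap costs an affected patient every change score for that measure. It needs the full chain in step 5, and the documents do not show how often that occurs. They therefore do not support reading it as a general loss of treated patients from the primary efficacy measure.

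**What to change.** 1. For the natural-history comparison, both descriptive and MMRM, open the V3 window at Day 93 in both groups. List treated patients' earlier scores, including early-discontinuation scores, separately. State whether this satisfies SAP 4.4.1.1 or amend that section explicitly.
2. For MFM and FVC only, define baseline as the last value up to Study Day 1 or, if there is none, the first-visit assessment completed on the permitted second consecutive day. State that such a value does not count as the post-baseline MFM required for the ITT population.
3. Reconcile Protocol 3.1.1.2 with Appendix 1 on whether MFM is done at screening.

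The cost is a few lines of text and slightly fewer Week 26 values, including the only post-baseline score of some early leavers.

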4.4.1 Primary Efficacy Endpoint

The primary efficacy outcome measure is the MFM D1+D2 score. MFM-32 is expected to be performed by all patients throughout study BN29854. If a patient erroneously performs the MFM-20 assessment at the baseline visit, MFM-20 scores will be derived from the post-baseline MFM-32 assessments performed by the patient, and analyses will be performed on this derived data. If MFM-32 is performed at baseline but MFM-20 is performed at one or more post-baseline visits, these assessments will be set to missing and only MFM-32 scores will be summarized. The assessment will be classified as MFM-32 if any item that is unique to the MFM-32 is reported, otherwise the assessment will be classified as MFM-20.

The MFM D1+D2 score is expressed as a percentage of the maximum possible score:

$$\text{MFM-32 D1+D2 score (\%)} = (\sum \text{MFM-32 D1 items scores} + \sum \text{MFM-32 D2 items scores}) * 100 / 75$$

$$\text{MFM-20 D1+D2 score (\%)} = (\sum \text{MFM-20 D1 items scores} + \sum \text{MFM-20 D2 items scores}) * 100 / 48$$

The change from baseline in the MFM D1+D2 score and the absolute value at each time-point will be summarized for the ITT population using descriptive statistics. Mean changes in the MFM D1+D2 score and corresponding 95% confidence intervals (CIs) over time will also be presented graphically. Summaries will be presented overall and by the treatment received in the previous Trophos study. Patients who only participated in study TRO19622CLEQ1115-1 and those who participated in study TRO19622CLEQ1275-1 will be summarized separately.

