4.4.1.1 Handling of Missing Data

- All observed assessments will be included in the analyses. No imputation for missing MFM scores will be performed.
- Following the death of a patient, MFM scores will be set to missing.
- If an individual MFM item is missing or was 'Not done,' the item will be set to zero in accordance with the MFM user manual.

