4.4.3.2 MFM Responders

Responder rates, where a responder is defined as no worsening from baseline in the MFM D1+D2 score, will be summarized at each time-point. The following assumptions will be made in the calculation of responder rates:

- Patients without an MFM assessment at a visit will be classified as non-responders. If a patient performs the MFM-20 instead of the MFM-32 at any post-baseline visit the assessment will be set to missing.
- Missing individual items will be imputed to zero.
- Patients who withdraw prematurely (for any reason) will be classified as non-responders.
- Patients who die during the study will be classified as non-responders.

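### In the exploratory responder analysis, a patient assessed with MFM-20 after an MFM-32 baseline is counted as a non-responder solely because of the form used, although the common D1+D2 items were observed at both times

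*SAP*

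**What the plan says.** SAP Section 4.4.1 foresees two form errors.

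- MFM-20 at baseline, MFM-32 later: "MFM-20 scores will be derived from the post-baseline MFM-32 assessments performed by the patient, and analyses will be performed on this derived data".
- MFM-32 at baseline, MFM-20 later: "these assessments will be set to missing and only MFM-32 scores will be summarized".

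A form is treated as MFM-20 when no item unique to the MFM-32 is reported. SAP Sections 4.1.4 (matched patients) and 4.4.4 (sensitivity analyses) also set a post-baseline MFM-20 to missing.

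In SAP Section 4.4.3.2 the endpoint is the responder rate, "where a responder is defined as no worsening from baseline in the MFM D1+D2 score, will be summarized at each time-point". Its first assumption has two parts: "Patients without an MFM assessment at a visit will be classified as non-responders", and then "If a patient performs the MFM-20 instead of the MFM-32 at any post-baseline visit the assessment will be set to missing". Together they make a post-baseline MFM-20 a non-response at that visit.

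The endpoint is exploratory (SAP Section 2.1.3; Protocol Section 2.6). SAP Section 4.4 plans no formal hypothesis test.

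**The concern.** Counting an absent patient as a non-responder is a familiar convention. Here the patient attended and was scored. The site used the shorter form, and the rule turns that error into a failure of treatment, even when every item on the form is unchanged or better than at baseline.

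The information needed to classify the patient is largely in hand. The SAP derives MFM-20 scores from MFM-32 forms in the other error case, so it treats the MFM-20 items as contained in the MFM-32. A baseline MFM-32 therefore supplies a baseline MFM-20 score.

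At stake is a one-directional bias in a descriptive rate. An affected patient who is truly a responder is always misclassified, and one who is truly a non-responder never is. More such errors can only lower the reported rate.

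**Working it through.** **1. Items available.** Each MFM item is scored 0 to 3 (Protocol Section 4.4.14.1). The D1+D2 denominators in SAP Section 4.4.1 are 75 for MFM-32 and 48 for MFM-20.

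- MFM-32: 75/3 = 25 items in D1+D2.
- MFM-20: 48/3 = 16 items in D1+D2.
- D1+D2 items not on the short form: 25 − 16 = 9.

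The total-score denominators in SAP Section 4.4.2.1 agree with the scale names: 96/3 = 32 and 60/3 = 20. The SAP's figures are thus reproduced.

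**2. Change on the common items.** For MFM-32 at baseline and MFM-20 at the visit:

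change = (sum of the 16 items at the visit − sum of the same 16 items at baseline) × 100/48

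No score has to be imputed. Responder status depends only on the sign of the change, so the factor 100/48 has no effect on it. As an invented example, a patient with a raw sum of 20 on these items at both times has a change of 0. That is no worsening on the common items, yet SAP Section 4.4.3.2 makes the patient a non-responder.

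**3. Why the scale matters for mean change.** One raw point is 100/75 = 1.33 percentage points on MFM-32 and 100/48 = 2.08 on MFM-20. Step 2 therefore suits a yes/no classification better than a mean change that mixes visits on the two forms.

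**4. Size per form.** With N patients in the denominator, one affected form lowers the rate by at most 100/N points. This maximum is reached only if the patient would have been a responder. If the form error is unrelated to response and the true rate is p, the expected loss is p × 100/N.

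The ITT size is not given. I use 119, the number of patients with analysed baseline samples from the previous randomised study (Protocol Section 1.2.2), as an assumption, and 171, the protocol maximum (Protocol Section 3.1.1). For p I use that study's Month 24 rates on the MFM total score, 56.3% on olesoxime and 38.6% on placebo (Protocol Section 1.2.2). They are illustrations only, since this endpoint is D1+D2.

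| N | Maximum per form | Expected, p = 56.3% | Expected, p = 38.6% |
|---|---|---|---|
| 119 | 100/119 = 0.84 | 56.3/119 = 0.47 | 38.6/119 = 0.32 |
| 171 | 100/171 = 0.58 | 56.3/171 = 0.33 | 38.6/171 = 0.23 |

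**5. Size by share of affected patients.** If a share m of patients has an MFM-20 at a visit, the reported rate is p(1 − m). The SAP gives no value for m and expects MFM-32 from every patient, so the shares below are assumptions.

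| m | Reported rate, p = 56.3% | Loss (points) | Loss, p = 38.6% (points) |
|---|---|---|---|
| 1% | 55.7% | 0.6 | 0.4 |
| 2% | 55.2% | 1.1 | 0.8 |
| 5% | 53.5% | 2.8 | 1.9 |
| 10% | 50.7% | 5.6 | 3.9 |

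**The case against.** The strongest reply is that the two form errors are not mirror images. With MFM-20 at baseline, no MFM-32 change exists at any visit, so rescoring is the only way to keep the patient. With MFM-32 at baseline, only the affected visit is lost. The SAP thus keeps each patient on one scale and uses MFM-20 only where nothing else is possible. Rescoring single visits would give a patient two baselines, although SAP Section 4.4 defines one baseline value, and would mix steps of 1.33 and 2.08 points within one trajectory. This stands for the change-from-baseline summary. It has no force for responder status, which uses only the sign of the change.

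A second reply is that nine of the 25 D1+D2 items are not seen. A loss confined to them would pass as no worsening, so affected patients would face an easier test than others. This also stands and is the price of the fix. The present rule has the larger fault, because it misclassifies every affected true responder.

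A third reply is that the rule is conservative. With no concurrent control arm and no test, there is little for conservatism to protect. Withdrawal and death are outcomes of the patient; use of the wrong form is not.

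Three stronger readings are tempting, and the documents do not support them.

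- A reader might infer that the primary MFM D1+D2 analysis also turns these visits into failures. It does not. SAP Section 4.4.1.1 imputes no missing score, so the cost there is a lost observation.
- A reader might set the discard against "All observed assessments will be included in the analyses" in SAP Section 4.4.1.1 and call it a contradiction. The discard in SAP Section 4.4.1 is a specific rule, and the general sentence can be read as subject to it.
- A reader might want common-item changes in the natural-history comparison. SAP Section 4.1.3 requires MFM-32 in the controls, and SAP Section 4.1.4 keeps MFM-20 out of the matched set. Treated MFM-20 changes would then be set against untreated MFM-32 changes in the model of SAP Section 4.4.1.2.

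**Conclusion.** The point holds for the exploratory responder analysis only, as a minor improvement. An assessed patient is counted as a non-responder because of the form used, and the resulting bias can only be downward.

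The loss is at most 0.84 percentage points per affected form at N = 119 and 0.58 at N = 171. The expected loss is about 0.47 or 0.33 points if the earlier study's 56.3% rate applies. These sizes rest on an assumed N, on a responder rate borrowed from the total score in another study, and on form errors being unrelated to response. A loss of several points would need several such forms at one visit, and the documents give no count that would suggest this.

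The claim that the common items are observed at both times rests on the SAP's own derivation of MFM-20 from MFM-32; the item lists are not in the documents.

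**What to change.** Change the first assumption in SAP Section 4.4.3.2, for patients with MFM-32 at baseline and MFM-20 at a visit:

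- Derive the baseline MFM-20 D1+D2 score from the baseline MFM-32, and classify the patient at that visit by the sign of the common-item change.
- Apply the zero rule for missing items only to items on the short form, not to the nine D1+D2 items that it does not contain.
- Flag these cases and report their number at each visit.
- Show the present rule, with these patients as non-responders, as a sensitivity result.

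The new text should also state the baseline form to which it applies. SAP Section 4.4.3.2 discards any post-baseline MFM-20, which read literally includes a patient with MFM-20 at both times, whereas SAP Section 4.4.1 discards it only after an MFM-32 baseline.

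Leave the primary change-from-baseline summary and the matched natural-history model on MFM-32 as written. At most, add a labelled common-item sensitivity summary of the change.

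The cost is a short change to one SAP section and an extra line or two in the responder table. The scoring is already needed for the other error case and would be applied to the baseline form instead of the later one. The price in validity is that a loss confined to the nine unseen items would be missed, which the flag and the sensitivity result make visible. The rule should be settled before the final analysis.
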